One strategy for enhancing engagement and completion of a brief intervention targeting perceived burdensomeness is to embed it within existing psychosocial treatments for youth psychopathology (e.g., cognitive-behavioral therapy [CBT] for youth anxiety disorders). Consistent with a modular CBT approach⁸, this strategy would enable clinicians to select and employ a brief intervention module when youth clients demonstrate thoughts of being a burden on others, with minimal disruption to the ongoing intervention protocol.

The purposes of this project are to (1) develop a novel, brief psychosocial intervention module (the GIVE module) targeting perceived burdensomeness towards others that can be embedded within existing CBT protocols for youth internalizing problems, and then (2) collect data relevant to the timing of reductions in perceived burdensomeness. The following aims will be pursued with N=30 clinic referred youths ages 10 to 17 who are receiving outpatient CBT for anxiety or depression.

Aim 1: Develop a manualized module targeting perceived burdensomeness to be used as an adjunct to existing psychosocial treatments. The GIVE module will consist of one core intervention session involving the youth and a parent (approx. 50 minutes) and one follow-up discussion of homework completion (approx. 10 minutes).

Aim 2: In an open trial, examine adherence and satisfaction with the GIVE module. Adherence, operationalized as provider fidelity and integrity, will be assessed by coding recorded session content. Youth and parent satisfaction will be assessed using the Client Satisfaction Questionnaire.

Aim 3: In an open trial, demonstrate reductions in youth levels of perceived burdensomeness. Perceived burdensomeness will be assessed at pretreatment (PRE), midtreatment (MID; i.e., CBT session 6), every treatment session, and posttreatment (POST). We expect that perceived burdensomeness will be significantly lower at POST relative to MID (i.e., CBT session 6, immediately before beginning the GIVE module).

APPROACH

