General overview. Following parental consent and youth assent, parents and youths will be administered interviews and questionnaires as part of PRE assessment to determine eligibility for this study (see Inclusion/Exclusion criteria). Eligible youths will be allocated to a 12-session CBT protocol with an additional module targeting perceived burdensomeness to be administered during CBT session 6. Youth participants' levels of perceived burdensomeness will be assessed weekly at the beginning of each session of the CBT protocol and again at a POST assessment one week after the final CBT session.

Participants. N=30 youths ages 10 to 17 years will be recruited upon entry into clinical services for anxiety and/or depression.

Inclusion criteria. To be included in this study, youth must: 1) be between ages 10 to 17 years old; 2) meet for a primary DSM-V diagnosis of an anxiety disorder, persistent depressive disorder, or major depressive disorder; 3) score ≥ 4 on the youth self-report Interpersonal Needs Questionnaire- Perceived Burdenomeness

Scale at PRE and again at CBT session 5; and 4) if youth have ADHD, tics, or impulse control problems, those disorders must receive an impairment rating no greater than 4 ('Moderate') on the 0–8 point scale on the Anxiety Disorders Interview Schedule Child/Parent versions (ADIS-C/P).

Exclusion criteria. Youth will be excluded from this study if they: 1) meet diagnostic criteria for Psychotic Disorders, Autism Spectrum Disorder or Intellectual Disability, 2) show high risk of imminent self-injurious behaviors, 3) are involved currently in another psychosocial treatment; 4) are not living with a primary caregiver who is legally able to give consent for the youth's participation, or 5) are a victim of previously undisclosed abuse requiring investigation or ongoing supervision by the Department of Social Services.

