The second component of the GIVE module is a home behavioral assignment to be planned in the subsequent 15 minutes of session 6. This home assignment is based on a brief online intervention developed by the sponsor⁷. In this brief at-home assignment, youths will identify one family member on whom they believe themselves to be a burden, and will design an activity to contribute to the well-being of that family member⁷ (usually the mother). This home assignment will be collaboratively planned during the session, including identification of barriers to completing the assignment and problem-solving aimed at improving completion of the assignment. Youths will already have been completing home assignments during previous CBT sessions and so the current home assignment should not impose new burden in terms of planning or execution. There will also be a brief discussion of this task in the beginning of the following session for approximately 5 minutes.

The third component of the GIVE module is a brief in-session parent-child relationship component. Unlike the first two components, the entirety of this component is done with both the youth and the parents present in the subsequent 15 minutes of session 6. This component begins with brief psychoeducation for the parent explaining parental acceptance and its implications in the context of perceived burdensomeness. Then, the parent will devise two lists: one that highlights the positive qualities of the child, and a second that includes ways that the parent can show acceptance and warmth. The inclusion of the third component is driven by research indicating that low parental acceptance fosters negative cognitive styles, and forthcoming research from our team indicating that low parental acceptance is significantly associated with youth perceptions of burdensomeness towards others¹⁸. There will also be a brief 5 minute wrap-up which encompasses review of the module and prevention (i.e., discussing the use of the module tools in forthcoming situations and experiences).

Measures.

Primary Outcome.

Interpersonal Needs Questionnaire- Burdensomeness Scale (INQ10-PB). The INQ10 is a widely used self-rated measure of perceived burdensomeness and thwarted belongingness. The burdensomeness subscale (INQ10-PB) consists of 6 Likert-type items. Prior research supports the convergent validity and internal consistency of the subscales in youth^{5, 20}.

Secondary Outcomes.

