Aim 3: Demonstrate reductions in youth levels of perceived burdensomeness. Reductions in levels of perceived burdensomeness will be examined using two approaches. In the first, a paired samples t-test will be conducted to examine changes in mean scores from MID (i.e., session 6 INQ10-PB score) to POST. A priori power analysis for the paired-samples t-test indicated that N=27 would provide sufficient power to detect a medium effect size, thus the current study would have adequate power. In the second, segmented regression analysis will be conducted by the applicant to preliminarily gain insight into the timing and maintenance of changes in levels of perceived burdensomeness. The segmented regression method is a powerful analysis for a quasi-experimental, interrupted time-series designs²⁸⁻²⁹, recommended for small samples²⁸. In segmented regression analysis, session to session assessments of perceived burdensomeness will be used to examine the slopes in perceived burdensomeness before and after intervention in CBT session 6. The intervention effect is examined by statistically comparing the PRE and POST intervention slopes. In an interrupted time-series design, it is recommended that observations be equally balanced between pre intervention and post intervention (e.g., 6 observations before and after), and for the PRE assessment variability to be reduced (e.g., only selecting youth with higher PB for the study) to maximize power²⁸. For this reason, there are six assessment points (administrations of INQ10-PB) planned prior to and after the administration of the module for a total of 12 observations, and only youth with elevated PB will be recruited (i.e., variability reduction). The segmented regression analysis is intended to be preliminary to gain insight into the timing of changes, and as such, may be underpowered by design.

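### If the INQ10-PB cut excludes youths at session 5 and the slopes are fitted to sessions 1–6 and 7–12, reusing the session 5 score biases the preliminary slope comparison toward a module effect

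*Combined protocol and SAP*

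**What the plan says.** The inclusion criteria (Approach) require that youths "score ≥ 4 on the youth self-report Interpersonal Needs Questionnaire- Perceived Burdenomeness" "Scale at PRE and again at CBT session 5". The Measures section says of the score only this: "The burdensomeness subscale (INQ10-PB) consists of 6 Likert-type items". It gives no item range and does not say whether items are summed or averaged.

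The General overview says that "levels of perceived burdensomeness will be assessed weekly at the beginning of each session of the CBT protocol". Under the Aim 3 statement, "Perceived burdensomeness will be assessed at pretreatment (PRE), midtreatment (MID; i.e., CBT session 6), every treatment session, and posttreatment (POST"). With 12 CBT sessions this makes 14 administrations. The session 6 score is taken before the module starts.

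In the SAP, Aim 3, "session to session assessments of perceived burdensomeness will be used to examine the slopes in perceived burdensomeness before and after intervention", and "The intervention effect is examined by statistically comparing the PRE and POST intervention slopes". The series has twelve points: "there are six assessment points (administrations of INQ10-PB) planned prior to and after the administration of the module for a total of 12 observations". The SAP does not list which of the 14 administrations these are, and names neither a level-change term nor a knot position. It presents the recruitment of youths with elevated scores as a way to reduce variability and does not mention regression to the mean. It calls the analysis preliminary and possibly underpowered.

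**The concern.** A score used to select people is, on average, partly high by chance among those selected. If the same score is then analysed as an outcome, it stands above the scores around it for reasons unrelated to treatment. Session 5 lies late in the pre-module segment. Raising it makes the pre-module decline look shallower, so the post-module slope looks steeper by comparison even if the module does nothing.

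The trial has one arm. The slope comparison is the only planned analysis that sets the course after the module against the same youths' course under CBT before it. A steepening produced by selection could be read as information about the timing of the module's effect.

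**Working it through.** **1. The plan's count.** Sessions 1–6 are scored before the module and sessions 7–12 after it: 6 + 6 = 12, as stated. Adding PRE and POST gives 7 + 7 = 14. Session-to-session scores and a total of 12 therefore point to sessions 1–6 | 7–12, where session 5 is the fifth pre-module point.

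**2. Can the cut exclude anyone?** Six items summed from a minimum of 1 give a lowest score of 6 × 1 = 6, above 4, so nobody is excluded. Summed from 0, the lowest score is 0 and the cut can bind. The documents do not settle this.

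**3. Weight of session 5 in the slope change (post minus pre).** Let d be the excess of the session 5 mean over the neighbouring sessions that selection causes. It is not the whole rise in the session 5 mean, because selection also raises every other session through stable differences between youths.
- Level-change term: sessions 1–6 have mean time 3.5 and sum of squares 17.5, so the weight is −(5 − 3.5)/17.5 = −0.0857.
- Knot at session 6, no level term: least squares gives −0.1014. With a knot at 6.5 it is −0.0857.

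**4. Worked case (assumed).** Cut at the clinic mean, stable between-youth share 0.6, independent residuals, no trend, no module effect, total SD 1. After both gates the session 5 mean is 0.906 SD and the other sessions about 0.678, so d = 0.906 − 0.678 = 0.228. The bias is 0.0857 × 0.228 = 0.020 SD per session with a level term, and 0.1014 × 0.228 = 0.023 with the knot at 6. Simulation gave −0.020 and −0.023. Rejection in the favourable direction with the level term, nominally 2.5%, was 6.8%.

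**5. Limit of the formula.** It is exact only for independent residuals. At autocorrelation 0.4 (share 0.5, cut +1 SD, no trend) the excess over sessions 1–3 is 0.39, and 0.0857 × 0.39 = 0.033, but the simulated bias is 0.054.

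**6. Range.** Assumed: N = 30, no module effect, total SD 1, PRE one week before session 1, stable share 0.5–0.85, residual autocorrelation 0 or 0.4. Each of 60 settings had 6,000 simulated trials, with a t-test on per-youth slope changes. Entries are two-sided rejection at nominal 5%, level term / knot at 6.

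| Cut relative to clinic mean | No CBT trend | Trend −0.05 SD per session |
|---|---|---|
| −1.5 SD | 5% / 5% | 5–6% / 5–6% |
| −0.7 SD | 5–6% / 5–7% | 5–8% / 5–9% |
| 0 | 5–9% / 6–11% | 7–14% / 8–18% |
| +0.5 SD | 6–13% / 7–16% | 8–19% / 9–26% |
| +1 SD | 7–18% / 9–24% | 9–29% / 11–40% |

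The mean slope change was negative, toward a module effect, in all 60 settings under both models.

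**7. Other layouts (level term).**
- PRE + 1–5 | 7–12: pre-module times 0–5 have mean 2.5 and sum of squares 17.5. The slope-change weights are +2.5/17.5 = +0.143 for PRE and −0.143 for session 5. With no trend and independent residuals the two gates give equal excesses, which cancel. In the other settings the bias was −0.001 to −0.046 SD per session (rejection 5–17%).
- 14 points: times 0–6 have mean 3 and sum of squares 28. The weights are +3/28 for PRE and −2/28 for session 5, a net +d/28. With d = 0.228 this is +0.008, against the module, and simulation agreed. With a trend and autocorrelation 0.4 it was −0.002 to −0.026.

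**8. Session 6 to POST t-test.** After removing the trend, rejection was 4.3–5.4% with independent residuals. At autocorrelation 0.4 there was a spurious drop of 0.01–0.27 SD, because session 6 carries part of the selected session 5 residual.

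**The case against.** The strongest reply is that the harm is hypothetical. The documents give no SD, reliability, trend, pass rate or scoring; the cut may exclude nobody; and the points are not listed, so the affected layout is a reading. On an assumed 0–36 sum with SD 6 and mean 6–14, a cut of 4 left a net slope change of only −0.016 to −0.079 points per session, at most 0.079/6 = 0.013 SD. (A floor effect works the other way there. Against selection at PRE only, session 5 selection contributed up to 0.079 + 0.033 = 0.112 points, or 0.019 SD.) The analysis is declared preliminary. Dropping session 5 also gives up the 6/6 balance that the SAP adopts on a cited recommendation.

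Most of this stands as a limit on scope and size. It does not remove the point: sessions 1–6 | 7–12 is the layout that best fits the SAP's wording, and the sponsor presents the selection as effective, since it is meant to reduce variability. Calling the analysis preliminary concedes low power, not bias in a known direction.

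A reader might infer that any exclusion by the cut biases the comparison toward the module. The documents do not support that: exclusion must occur at session 5, not only at PRE, and the direction depends on the layout. Nor should the 29% and 40% be taken as expected error rates. They need a cut 1 SD above the clinic mean, a stable share of 0.5, autocorrelation 0.4 and a declining trend together, and nothing in the documents shows such a setting.

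**Conclusion.** The point holds under two conditions: some youths fail the cut at session 5, and the series is sessions 1–6 | 7–12. Regression to the mean then biases the slope difference toward a module effect, by 0.086d or 0.101d per session with independent residuals. The size cannot be fixed from the documents. Under the assumptions above, rejection is at most about 8–9% for cuts below the clinic mean and becomes material only for cuts at or above it. The bias is zero if nobody is excluded at session 5, about zero for PRE + 1–5 | 7–12 with independent residuals and no trend, and can reverse in a 14-point series.

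A reader might extend this to the trial's main test of reduction. That is not supported: the powered session 6 to POST t-test does not use session 5 and is touched only through autocorrelation. Nor are the unlisted points and model terms a separate error. The SAP gives the count, the session 6 boundary and the slope contrast; the missing details matter here because the direction of the bias depends on them. This is a worthwhile, inexpensive improvement, held with medium confidence.

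**What to change.** In the SAP, Aim 3:

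1. Fit the main slope comparison without the gated scores: pre-module sessions 1–4 and 6, post-module sessions 7–12, with PRE left out.
2. Allow autocorrelated within-youth residuals.
3. Report the 12-point fit as a sensitivity analysis, labelled as subject to regression to the mean.
4. Report how many PRE-eligible youths fail at session 5. If none do, this bias is absent.
5. In support of these, list the points, the model terms (level change or not, knot position), the INQ10-PB item range, and whether the score is a sum or a mean.

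The cost is SAP wording and some precision, with no extra visits or data. With a level term the variance factor goes from 2/17.5 = 0.11429 to 1/14.8 + 1/17.5 = 0.12471, so the slope-change standard error rises by √(0.12471/0.11429) = 1.045, or 4.5%. With the knot at 6 it is √(0.12464/0.11194) = 1.055, and with the knot at 6.5 √(0.12307/0.11429) = 1.038. The 6/6 balance becomes 5/6.

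The remedy is partial. With independent residuals it removes the bias (rejection 4.4–5.4%). At autocorrelation 0.4, with cuts at or above the clinic mean, it removes only about 35–65%, because session 6 still carries part of the selected residual. The regression-to-the-mean caveat should therefore accompany the main fit as well.
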